4.1.4 Data Derivation

4.1.4.1 Imputation of missing or partial AE or concomitant medication dates

The following rules will apply in the situation of missing or partial AE or concomitant medication dates.

For partial start date:

- If the year is unknown, then do not impute the date but assign a missing value.
- If the month is unknown, then:
 - If the year matches the year of the first dose date, then impute the month and day of the first dose date.
 - Otherwise, assign 'January'.
- If the day is unknown, then:
 - If the month and year match the month and year of the first dose date, then impute the day of the first dose date.
 - Otherwise, assign '01'.

For partial end date:

- If the year is unknown, then do not impute the date but assign a missing value.
- If the month is unknown, then assign 'December'.
- If the day is unknown, then assign the last day of the month.

After implementing the rules above, to determine whether AEs (or medications) with missing start or stop dates are pretreatment or on/after treatment the following strategy will be used:

- If the start date and stop date are both missing, then the most conservative approach will be taken and the AE (or medication) is considered to be treatment-emergent (or concomitant).
- If the start date is missing but the stop date is not missing and is after the day of study dose administration, then the most conservative approach will be taken and the AE (or medication) is considered to be treatment-emergent (or concomitant).
- If the start date is missing but the stop date is not missing and is on or before The day of study dose and after the date of signed informed consent, then the AE (or medication) is considered to be pretreatment (or prior).

•

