3.9 Safety Assessments

3.9.1 Adverse Events

An Adverse Event (AE) is any new untoward medical occurrence or worsening of a preexisting medical condition in a clinical investigation subject administered an investigational medicinal product, even if it does not have a causal relationship with that product. Any unfavorable or unintended sign, symptom, or disease temporally associated with the use of the study agent, whether or not it is considered study agent-related will be considered an AE. This includes any newly occurring event or previous condition that has increased in severity or frequency since the administration of the study agent.

Monitoring for AEs will occur from the time of informed consent until the patient completes the study. The post-dosing observation period will begin with an 8-day inpatient stay (Days 0 to 7). This inpatient stay can be extended and requires that at least 2 days elapse from the resolution of any signs of infection or serious AEs (SAEs) before discharge.

All Grade 3 and 4 clinical laboratory results that represent an increase in severity from baseline will be reported as AEs. A Grade 1 or 2 clinical laboratory abnormality should be reported as an AE only if it is considered clinically significant by the investigator.

All AEs, including observed or volunteered problems, complaints, or symptoms from the time of informed consent until 8 weeks post-dose are to be recorded, regardless of causality. After 8 weeks post-dose, only AEs with possible, probable, or definite relationship to the study agent will be reported with follow up as noted above for AEs within the first 8 weeks post treatment.

Adverse events will be evaluated against the baseline history and physical examination and intensity graded using the NCI CTCAE, Version 4.0, which can be accessed at http://ctep.cancer.gov/reporting/ctc.html.

All AEs experienced by a patient, irrespective of the suspected causality, will be monitored until the event has resolved or stabilized, until any abnormal laboratory values have returned to baseline or stabilized at a level acceptable to the PI or local investigator and Medical Monitor, until there is a satisfactory explanation for the changes observed, or until the patient is lost to follow-up.

A Serious Adverse Event (SAE) is any AE, occurring at any dose and regardless of causality that:

• Results in death.

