4.5 Safety Evaluation

4.5.1 Adverse Events (AEs)

Adverse Events will be mapped to the Medical Dictionary Regulatory Activities (MedDRA), Version 14.1 with the lowest level term that most accurately reflects the adverse event.

Adverse events will be categorized as:

- Treatment emergent adverse event (TEAE): A treatment-emergent adverse event is defined as any event not present prior to the initiation of the treatments or any event already present that worsens in either intensity or frequency following exposure to the treatments.
- Non-treatment emergent adverse events (NTEAE): An AE that occurred before the first administration of IMP and did not worsen in severity or frequency after IMP exposure.

All adverse event data recorded on the eCRFs will be listed by dose level and patient. Included on the AE listing will be the adverse event, start date and time, outcome, stop date and time, CTCAE grade, relationship to study drug, action taken, whether the AE was serious, whether TEAE, whether or not a concomitant medication was taken, time of AE onset relative to IMP dosing and AE duration.

All serious adverse events will be listed. A listing of all AEs leading to treatment discontinuation will be presented. Details of death and hospitalization relating to serious adverse events will be listed.

As defined in the protocol, all adverse events will be assigned a CTCAE grade of 1 to 5.

Unless specified otherwise, all adverse event summaries will include the TEAEs only. In these summaries the count of AEs will be the number of patients reporting adverse events and not the number of events reported. If the same AE (preferred term) is reported several times for the same patient, it will only appear once for that specified dose level in the summary tables. For patients with multiple adverse events of the same preferred term and of different intensity, the highest intensity assessment will be used in summaries presented by intensity.

For purposes of the summary tables, AEs will be classified as either being related to IMP or not related. AEs related to IMP will include AEs classified as 'Definite', 'Probable', or 'Possible'. AEs not related to IMP will include AEs classified as 'Not Related' or 'Unlikely'.

Frequency counts will be categorized and displayed by the MedDRA system organ class and preferred term.

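### Partial AE start dates are set to the dose date without checking a known stop date, so a screening event that ended before dosing can be counted as treatment-emergent

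*SAP*

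**What the plan says.** SAP section 4.1.4.1 imputes partial start dates before anything is classified. With the day unknown: "If the month and year match the month and year of the first dose date, then impute the day of the first dose date". With the month unknown: "If the year matches the year of the first dose date, then impute the month and day of the first dose date". If the known parts do not match the dose date, the missing parts go to the first of the month or to January.

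A second set of rules follows, to be applied after those imputations: "to determine whether AEs (or medications) with missing start or stop dates are pretreatment or on/after treatment the following strategy will be used". They use the stop date, but only for an AE or medication that still has a missing date. If both dates are missing, or the start is missing and the stop falls after the dosing day ("If the start date is missing but the stop date is not missing and is after the day of study dose administration"), the record is treatment-emergent or concomitant, and the SAP calls this conservative. If the start is missing and the stop "is on or before The day of study dose and after the date of signed informed consent", the record is pretreatment or prior.

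Section 4.5.1 defines a treatment-emergent AE (TEAE) as "any event not present prior to the initiation of the treatments or any event already present that worsens in either intensity or frequency" after exposure. Its counterpart, the non-treatment-emergent AE, began before the first administration and did not worsen afterwards. AE summaries are restricted to TEAEs unless stated otherwise, and count patients. Section 4.5.8 classes a medication as prior if it stopped before administration, and as concomitant if it stopped at or after it.

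**The concern.** AEs are collected from informed consent (section 3.9.1), and screening may run for 21 days before dosing (section 3.1), so AEs that resolve before the injection will be in the database. Moving an uncertain start date to the dose date is a sensible cautious default when nothing else is known. It is not sensible when the recorded stop date shows that the event was over before exposure. The derived record then contradicts itself, with a start after its stop, a negative duration and a TEAE flag on an event that cannot have emerged on treatment.

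TEAE tables by dose level are a main safety output, and the planned cohorts have 3 to 6 patients. A single wrong flag is therefore visible in a cohort percentage. The AE listing in section 4.5.1 shows onset relative to dosing, duration and TEAE status, so the inconsistency would also appear in the listing and have to be explained.

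**Working it through.** The SAP states no figure on this point, so there is none to reproduce. The check applies the rules of section 4.1.4.1 in their stated order, then classifies by start date (on or after dosing = TEAE).

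**Test cases, dose on 20 March 2016**

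| Recorded start | Recorded stop | Start after imputation | Class |
|---|---|---|---|
| unknown day, March 2016 | 5 March | 20 March | TEAE, start after stop |
| unknown day and month, 2016 | 5 March | 20 March | TEAE, start after stop |
| wholly missing | 5 March | missing | pretreatment |
| wholly missing | 20 March (dosing day) | missing | pretreatment |
| unknown day, March 2016 | 20 March (dosing day) | 20 March | TEAE |
| wholly missing | 21 March | missing | TEAE |

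In rows 1 and 2, stop minus start is 5 − 20 = −15 days. Comparing rows 1 and 3, knowing more about the start date produces the wrong class and knowing nothing produces the right one. Comparing rows 4 and 5, the same stop date gives opposite classes.

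**How often the match occurs, given a partial date.** This is illustrative. It takes every dose day in a 365-day year and gives equal weight to every start/stop pair in which the AE starts *a* days before dosing (*a* = 1 to 21) and stops between then and the day before dosing.

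- Pairs per dose day: 1 + 2 + … + 21 = 231. Total: 365 × 231 = 84,315.
- Sum of *a*² for 1 to 21: 21 × 22 × 43 / 6 = 3,311.
- Day unknown: the start falls in an earlier month than dosing for 12*a* of the 365 dose days. Share wrongly made TEAE: 1 − 12 × 3,311 / 84,315 = 0.529, or 53%.
- Month and day unknown: the start falls in an earlier year for *a* of the 365 dose days. Share: 1 − 3,311 / 84,315 = 0.961, or 96%.

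These are shares of resolved screening AEs that already have a partial start date. They are not shares of all AEs.

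**Effect on a table.** One patient is 1/6 = 17% of a cohort of six and 1/3 = 33% of a cohort of three.

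**Dosing-day stop.** For medications, section 4.1.4.1 makes a record with a missing start and a dosing-day stop prior. Section 4.5.8 makes a medication that stopped on dosing day, at or after administration, concomitant. For AEs, the rule could class as pretreatment a reaction that began and ended on the day of injection, whereas the two neighbouring rules lean towards treatment-emergent.

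**The case against.** Four points can fairly be made for the plan.

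- **The text is damaged.** In the copy available, section 4.1.4.1 ends in an empty bullet, and a stray fragment appears under section 4.1.4.2. The full rule, and any stop-date clause in it, cannot be read. What survives says that AEs are classified by start date, which agrees with the reading used here. The caveat stands.
- **The definition should govern.** By section 4.5.1, an AE that ended before dosing is not treatment-emergent, so a careful programmer might override the imputed date. That shows the conflict but does not resolve it, because the imputation rule has no such exception.
- **The cases are uncommon and the main error is visible.** The first needs a partial start date on a prospectively collected AE with a known earlier stop. The second needs an unknown start year for an event ending on Day 0 in a closely monitored inpatient, which is remote. The first error over-counts rather than hides events, and section 4.1.2 keeps raw dates in the listings. All of this limits the size.
- **Dose escalation is hardly exposed.** A reader might infer that dose-limiting toxicity counts are affected. The SAP does not support that: the grade-based criterion requires at least a possible relation to study agent, and the other concerns infection by the agent. An event resolved before injection should meet neither.

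A reader might also infer that the TEAE tables misclassify late events, because TEAE has no end date and "After 8 weeks post-dose, only AEs with possible, probable, or definite relationship to the study agent will be reported". The SAP does not support this either. A late related AE is correctly a TEAE. The asymmetry comes from the collection rule, and no planned table reports the share of AEs judged related. Any estimate of distortion would rest on event rates that the SAP does not give.

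**Conclusion.** The point holds as a narrow error of date logic. Where the known parts of a partial start date match the dose date, the SAP's rules give an AE that ended before dosing a start after its stop and a TEAE status, contrary to its own definition in section 4.5.1. The dosing-day boundary for wholly missing starts is a lesser inconsistency: it contradicts section 4.5.8 for medications and is not conservative for AEs.

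The SAP gives no frequency for either case, and both are likely to be infrequent. When one occurs, a single patient moves a cohort percentage by 17 to 33 points. The 53% and 96% figures describe only how easily the first rule goes wrong once a partial date exists, under uniform dates. The conclusion assumes that the unreadable last bullet of section 4.1.4.1 contains no stop-date exception. It does not extend to the dose-escalation decisions or to the handling of AEs after 8 weeks.

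**What to change.** Add two sentences to SAP section 4.1.4.1.

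1. If the known stop date is before dosing, the imputed start may not be later than the stop date (cap it there, and not earlier than consent), and the AE is classified as pretreatment.
2. If the start date is wholly missing and the stop date is the dosing day, classify the AE as treatment-emergent and the medication as concomitant, unless the stop time is known to precede injection.

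With the first change, none of the resolved screening AEs enumerated above becomes a TEAE. With the second, sections 4.1.4.1 and 4.5.8 agree for medications. The last bullet of section 4.1.4.1 should be checked in the source file when the text is edited.

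The cost is two sentences and minor programming, with no new table. Optionally, a footnote to the TEAE tables can say that only related AEs are collected after 8 weeks; the tables need not be cut at that point.

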Note: In the case of Stable Disease, measurements must have met the Stable Disease criteria at least once after study entry at a minimum duration of stable disease lasting 8 or more weeks.

4.1.4.3 Nadir

Nadir for injection lesion is defined as the smallest sum of the longest diameters of each injection lesion since start of treatment.

4.2 **Patient and Treatment Information**

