3.1 General Considerations - Summary of Study Design

Patients who provide informed consent will be screened within 21 days prior to *C. novyi*-NT spore administration. Patients will report to the clinical site within 24 hours of Day 0 to reconfirm eligibility and for baseline assessments. Eligible patients will be admitted and enrolled sequentially into a dosing cohort as described in the section 3.6 of this SAP.

Spore dose administration will occur on Day 0, and patients will remain in-house for observation through Day 7 (a total of 8 days). Patients will return to the clinical site for follow-up visits at the following time points: Days 11, 14 (Week 2), 18, 21 (Week 3), 25, 28 (Week 4) and 2, 4, 8, and 12 months post-dose. Assessment of safety, efficacy, and

disposition of *C. novyi*-NT will be performed at scheduled time points throughout the study.

A standard "3+3" dose escalation will be used. The following definitions and rules will be employed:

- Toxicity Criteria will be those listed in the National Cancer Institute (NCI) Common Terminology Criteria for Adverse Events (CTCAE), Version 4.0, which is available at http://ctep.cancer.gov/reporting/ctc.html
- An adverse event (AE) of Grade 3 toxicity lasting three (3) days or longer or Grade 4 toxicity of any duration that is assessed to be at least possibly related to study agent will be considered a DLT. Signs and symptoms of *C. novyi*-NT infection which are associated with a Sequential Organ Failure Assessment (SOFA) score > 5 that require invasive intervention including percutaneous drainage of an abscess or that result in prolonged hospitalization (> 5 days) will also qualify as DLTs.
- DLT assessment period is defined as 4 weeks after dosing of the last patient in a cohort.
- Toxicity will be assessed from administration of study agent up to 8 weeks.
- The dose escalation rules, as outlined in Table 1, will be applied.
- Additional patients will be enrolled at the MTD to achieve a total of six patients at that dose level if fewer than six patients were treated previously at that dose.
- Doses will be increased in successive cohorts until the MTD is reached or until complete germination and tumor regression occurs, making higher doses unnecessary.
- The MTD (or dose at which complete germination and tumor regression occurs) will be the recommended dose for future Phase II *C. novyi*-NT IT administration studies.

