3.10 Efficacy Assessments

Tumor response and progression will be evaluated using the international criteria proposed by the Response Evaluation Criteria in Solid Tumors (RECIST) Committee (version 1.1: http://www.eortc.be/recist/).

Objective response will be measured by serial CT or MRI scans of the injected tumor and site of metastatic involvement. Overall response, using CT/MRI scan results, will be based on observation of measurable and non-measurable disease as compared to baseline and nadir in target and non-target lesions per RECIST 1.1 at screening and at follow-up times 1 to 12 months post dose.

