3.10.1 Tumor Response

3.10.2 Computed Tomography (CT) or MRI Scans

Objective responses will be measured by serial CT or MRI scans of the chest, abdomen, pelvis, and any other sites of metastatic involvement.

CT or MRI scans will be performed at screening, Day 7, and at follow-up times (28 days, and 2, 4, 8 and 12 months post-dose). However, Day 7 CT/MRI is not used for tumor response assessment. It is used for abscess assessment to see if the patient can be discharged.

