3.10.3 Response Evaluation Criteria in Solid Tumors (RECIST)

Tumor evaluation per RECIST including targeted injection lesion response and overall response will be evaluated.

Target lesion measurements will be assessed at Screening, and at Months 1, 2, 4, 8, 12. The injection lesion response and overall response will be evaluated at Months 1, 2, 4, 8, and 12.

Target lesion measurements will record the lesion number, location code, description of lesion, evaluation, days after dose administration, date of evaluation, method of evaluation, and the lesions' longest diameter (cm). The tumor response will categorize the lesion response as one of the following: complete, partial, stable, progressive, or unknown.

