4.1.2 Data Presentations

Data for all enrolled patients who received any amount of IMP will be presented in the data listings. Table summaries will only include those patients that received IMP.

For those listings or data summaries where baseline and change from baseline measurements will be presented, the last observed measurement prior to dosing on Day 0

will be considered the baseline measurement if collecting at both screening and Day -1 to Day 0 pre-dose.

All pre- and post-dose assessments including all unscheduled assessments will be included in the data listings. For pre-dose assessments, the last assessment (including unscheduled) taken for a time point will be used in the data summaries (summary tables, figures, and statistical analysis); for all post-dose time points, the original assessment for any given time point will be used in the data summaries (summary tables, figures, and statistical analysis).

Continuous data will be described using descriptive statistics: number of observations (N), mean, median, standard deviation (SD), minimum and maximum. Frequencies and percentages will be used for summarizing discrete (categorical) data. The denominator for all percentage, unless otherwise specified, will be the number of patients in a given cohort.

Data that are reported as missing will be excluded from all descriptive and nondescriptive data analysis. Observations that are spurious (extreme relative to the majority of the data) will not be altered or removed from any presentation of the data without agreement from the sponsor.

For data listings, all raw data will be reported/displayed exactly as provided. For summaries of quantitative data, the minimum and maximum value will be reported exactly as the raw data are reported; measures of central tendency (means, medians) will be reported to one more decimal place than the raw data; measures of variance (SD) will be reported to two more decimal places than the raw data.

Unless specified otherwise, data collected over time will be listed by cohort, dose level, patient number, and time point (where applicable). Unless specified otherwise, all tables and figures will be presented by dose level. The Summary of Tables, Figures and Listings in the attachment section might be updated later if needed. In this SAP, treatment will refer to any of the following planned categories of *C. novyi*-NT dose level:

- $1 (x \ 10^4 \text{ spores})$
- $3 (x \ 10^4 \text{ spores})$

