4.3 Efficacy Analysis

Results of the CT and/or MRI scans will be listed by dose level and time points for each patient.

Results of the injection lesion evaluation, the overall response assessment, and the best overall response assessment per RECIST will be listed by dose level and time points.

Summary table for individual patient data for injection lesion measurements will present descriptive statistics by dose level and time point for the lesions' longest diameter (cm),

including % reduction in injection lesions' longest diameter (cm) from baseline and nadir.

The overall lesion response will be summarized using the number and percentage of patients by dose level and time point within each of the categories: complete, partial, stable, progressive, or unknown.

The best overall lesion response will be summarized using the number and percentage of patients by dose level within each of the categories: complete, partial, stable, progressive, or unknown.

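### The injected-lesion nadir leaves out the screening baseline and names no visit window, so change from nadir is understated for lesions that grow from the first scan (minor)

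*SAP*

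**What the plan says.** Section 4.1.4.3 gives the SAP's only definition of nadir, and gives it for the injected lesion alone: "Nadir for injection lesion is defined as the smallest sum of the longest diameters of each injection lesion since start of treatment".

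The timing of treatment and of measurement is set elsewhere:

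- Section 3.1: "Spore dose administration will occur on Day 0".
- Section 3.10.3: "Target lesion measurements will be assessed at Screening, and at Months 1, 2, 4, 8, 12".
- Section 3.10.2: "However, Day 7 CT/MRI is not used for tumor response assessment".
- Section 4.1.2 takes as baseline "the last observed measurement prior to dosing on Day 0". For lesion size, that is the screening measurement.

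Nadir is then used in two places. Section 4.3 describes the injected-lesion summary (Table 14.2.1.3) as "including % reduction in injection lesions' longest diameter (cm) from baseline and nadir". Section 3.10 describes overall response "as compared to baseline and nadir in target and non-target lesions per RECIST 1.1".

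**The concern.** A nadir is the reference against which regrowth is measured. If it can be drawn only from post-dose scans, a lesion that enlarges from the first scan is compared with a value that is already enlarged, and its growth looks smaller than it is. The pattern is foreseeable here, because the SAP itself allows for local inflammation and abscess at the injected site (sections 3.9.1 and 3.11.2).

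The second gap is the visit window. Two programmers could both follow section 4.1.4.3 and produce different values in Table 14.2.1.3.

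Anti-tumor activity in the injected lesion is a stated objective (section 2). With 3 to 6 patients per cohort (section 3.5), one distorted value can visibly move a cohort summary.

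**Working it through.** The SAP states no figure on this point, so there is none to reproduce. The lesion sizes below are illustrative assumptions.

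**Which measurements can enter the nadir.** Treatment starts on Day 0 (3.1). Screening lies before it, and Day 7 is excluded from response (3.10.2). The scheduled candidates are therefore Months 1, 2, 4, 8 and 12 (3.10.3).

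**Formula.** % change = 100 × (current − reference) / reference. The SAP's % reduction is the same number with the sign reversed. Four references are compared:

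- (a) minimum over all post-dose visits;
- (b) post-dose minimum up to and including the current visit;
- (c) minimum over earlier post-dose visits only;
- (d) as (c), with baseline added.

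Readings (a) to (c) all fit the literal text.

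**Growing lesion: baseline 5.0 cm, then 5.9, 6.9 and 8.1 cm**

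| Visit | From baseline | (a), (b) | (c) | (d) |
|---|---|---|---|---|
| Month 1 | 5.9/5.0: +18.0% | 0% | undefined | +18.0% |
| Month 2 | 6.9/5.0: +38.0% | 6.9/5.9: +16.9% | +16.9% | +38.0% |
| Month 4 | 8.1/5.0: +62.0% | 8.1/5.9: +37.3% | +37.3% | +62.0% |

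All three literal readings understate growth from nadir at Months 2 and 4. Column (d) equals the change from baseline, as it must when baseline is the smallest value.

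**Shrinking lesion: baseline 5.0 cm, then 4.0, 3.0 and 2.5 cm**

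| Visit | From baseline | (a) | (b) | (c) | (d) |
|---|---|---|---|---|---|
| Month 1 | −20.0% | (4.0−2.5)/2.5: +60.0% | 0% | undefined | −20.0% |
| Month 2 | −40.0% | (3.0−2.5)/2.5: +20.0% | 0% | −25.0% | −25.0% |
| Month 4 | −50.0% | 0% | 0% | (2.5−3.0)/3.0: −16.7% | −16.7% |

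Reading (a) shows growth of 60% and 20% in a lesion that only shrinks.

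**Shrinking, then regrowing: baseline 5.0 cm, then 4.0, 3.0, 3.8 and 4.5 cm.** From Month 2 onward (c) and (d) agree: −25.0%, +26.7%, +50.0%. Leaving out baseline does no harm once the lesion has been at or below baseline at an earlier visit.

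**How general this is.** All combinations of a baseline and five post-dose sizes, each 2, 3, 4, 5 or 6 cm, give 5 × 5⁵ × 5 = 78,125 visit values. From the second post-dose visit onward, (c) and (d) differ in 14,270 values. In every one, (c) is too low and baseline is smaller than every earlier post-dose value. A reduction from nadir is positive in none of the 78,125 values under (a) or (b), and in 14,270 under (c). The grid shows when the definitions part; it does not estimate how often that would happen in patients.

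**The case against.** The strongest reply is that nothing is hidden. Section 4.3 reports change from baseline alongside change from nadir, "longest diameter (cm) from baseline and nadir". In exactly the affected patients, change from baseline equals change from a corrected nadir. The diameters are summarised too, and efficacy is descriptive. This reply stands, and it limits the severity. It does not make the nadir value correct.

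A reader might infer three stronger things, none of which the SAP supports.

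- *That a reduction from nadir can never be positive.* This is true under (a) and (b) but false under (c), and the text does not choose between them.
- *That a non-positive reduction conceals growth.* It does not: growth appears as a negative reduction, which is an awkward label. The understatement comes from leaving out baseline. Reading (a) errs the other way and can overstate growth.
- *That progression is delayed and growing lesions are counted as stable.* This needs the section 4.1.4.3 nadir to be the progression reference, which the SAP does not say. Section 3.10 refers response to RECIST 1.1 and names baseline as a comparator as well as nadir. Best overall response in section 4.1.4.2 is built from visit-level overall responses. The SAP restates no progression threshold. If this nadir were the only reference, any assumed threshold above 18.0% and up to 37.3% would move progression in the growing example from Month 2 to Month 4. The sizes were chosen to show that, so it is a conditional illustration only.

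**Conclusion.** The definition needs correcting, and the severity is minor. Read literally, section 4.1.4.3 excludes the screening baseline and leaves the visit window open. Growth from nadir is then understated for any injected lesion larger than baseline at every earlier post-dose visit: +17% against +38% at Month 2 in the example. Month 1 change from nadir is zero or undefined for every patient unless nadir covers all follow-up. Under that reading, a shrinking lesion shows false early growth.

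The conclusion rests on the literal wording and on the measurement schedule. The size rests on assumed lesion diameters. The error affects one descriptive statistic in Table 14.2.1.3. No dose-escalation rule in section 3.1 uses it, and an effect on response categories is possible only if this nadir is also applied there.

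**What to change.** Replace the definition in section 4.1.4.3 with: *Nadir at a visit is the smallest longest diameter of the injected lesion among baseline and all earlier post-dose response assessments (Day 7 excluded).*

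In section 4.3 and Table 14.2.1.3, report *% change from baseline* and *% change from nadir* in place of % reduction, so that growth is positive and shrinkage negative.

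The cost is one sentence, one derivation and a column label. No new data are needed: the efficacy set in section 4.1.1 already requires a baseline tumor assessment, so the corrected nadir is defined from Month 1 wherever the injected lesion was measured at baseline.
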